3 STUDY OBJECTIVES

3.1 Primary objective

The primary objective is to evaluate the PK of BRV in neonates who have seizures that are not adequately controlled with previous AED treatment, and to identify the optimal BRV dose (Exploratory Cohort) for the treatment of subjects enrolled into the Confirmatory Cohorts of this study.

3.2 Secondary objectives

The secondary objectives are:

- To evaluate the efficacy of BRV in severe and nonsevere seizure burden (defined as total minutes of ENS per hour) in neonates with seizures that are not adequately controlled with previous AED treatment
- To evaluate the short-term safety and tolerability of BRV in neonates

4 STUDY VARIABLES

4.1 PK variables (Exploratory and Confirmatory Cohorts)

4.1.1 Primary PK variable

The primary PK variable is as follows:

- Plasma concentrations of BRV following first dose on Day 1

4.1.2 Other PK variables

- Plasma concentrations of BRV on other occasions
- Plasma concentrations of BRV metabolites ucb-42145 (acid), ucb-100406-1 (hydroxy), and ucb-107092-1 (hydroxyacid)
- AUC, volume of distribution, and clearance of BRV
- Plasma concentrations of concomitant AEDs if administered

4.2 Efficacy variables (Confirmatory Cohorts only)

The variables for the evaluation of BRV efficacy are described in Section 4.2.1 (Secondary efficacy variables) and Section 4.2.2 (Other efficacy variables).

4.2.1 Secondary efficacy variables

The main secondary efficacy variable is as follows:

- Proportion of responders to BRV treatment from Baseline to 3 hours after the initial BRV dose

A BRV responder is defined as a subject who achieves the following reduction in seizure burden (ENS in minutes per hour) without need for rescue medication, compared to the seizure burden measured during the Baseline Period immediately prior to BRV administration, evaluated for a 2-hour period starting 1 hour after the start of initial BRV treatment:

- At least 80% reduction in nonsevere seizure burden

(Nonsevere seizure burden is defined as $\leq 50\%$ seizure activity on VEEG in all 30-minute timespans)

OR

- At least 50% reduction in severe seizure burden

(Severe seizure burden is defined as $> 50\%$ seizure activity on VEEG in any 30-minute timespan). Timespans of 30 minutes refer to the following intervals within the 2-hour period: 0 to ≤ 30 minutes, > 30 to ≤ 60 minutes, > 60 to ≤ 90 minutes, and > 90 to ≤ 120 minutes.

For this study, an ENS is defined as an EEG seizure lasting for at least 10 seconds on VEEG. Baseline seizure burden is defined as seizure burden measured on the continuous VEEG (total ENS in minutes per hour) during a period of up to 1 hour immediately prior to the first administration of study drug.

In addition, the secondary efficacy variables will include:

- Proportion of subjects with at least 80% reduction in nonsevere seizure burden from Baseline to 3 hours after the initial BRV treatment
- Proportion of subjects with at least 50% reduction in severe seizure burden from Baseline to 3 hours after the initial BRV treatment
- Absolute reduction in average seizure burden measured by continuous VEEG from Baseline to the end of the 96-hour Evaluation Period
- Percent reduction in average seizure burden measured by continuous VEEG from Baseline to the end of the 96-hour Evaluation Period
- Proportion of BRV responders at the end of the 96-hour Evaluation Period
- Proportion of subjects who are seizure-free (100% reduction in seizure burden from Baseline) at 24 hours following the start of initial BRV treatment, categorized by subjects with nonsevere or severe seizure burden at Baseline

- Time to reduction in seizure burden for BRV responders (defined as the first timepoint when BRV responder criteria are met)
- Seizure freedom at the end of the Down-Titration Period
- Rate of at least 50% reduction in ENS frequency per hour from Baseline to the end of the 96-hour Evaluation Period
- Proportion of subjects who are seizure-free by time interval at 3 hours, at 3-hour intervals thereafter through 24 hours, and every 12 hours to 24 hours thereafter up until the end of the 96-hour Evaluation Period following the start of the initial BRV treatment
- Absolute difference in clinical seizures at the end of the 24-hour Evaluation Period from Baseline for neonates with motor seizures at the time of inclusion
- Percent difference in clinical seizures at the end of the 24-hour Evaluation Period from Baseline for neonates with motor seizures at the time of inclusion

The use of rescue medication will affect the analysis of the main secondary efficacy variable (see Section 13.5.1). The factors affecting the definition of BRV responders for the analysis of the secondary efficacy variables are described in Section 10.1.

4.2.2 Other efficacy variables

Other efficacy variables will include:

- Absolute reduction from Baseline in seizure burden at evaluation periods of 0 hours to 3 hours, >3 hours to 6 hours, >6 hours to 12 hours, >12 hours to 24 hours, >24 hours to 36 hours, >36 hours to 48 hours, >48 hours to 72 hours, and >72 hours to 96 hours after the start of initial BRV treatment
- Percent reduction from Baseline in seizure burden at evaluation periods of 0 hours to 3 hours, >3 hours to 6 hours, >6 hours to 12 hours, >12 hours to 24 hours, >24 hours to 36 hours, >36 hours to 48 hours, >48 hours to 72 hours, and >72 hours to 96 hours after the start of initial BRV treatment
- Categorized percentage reduction from Baseline to the end of the 96-hour Evaluation Period in seizure burden (<-25% [worsening], -25% to <25% [no change], 25% to <50%, 50% to <80%, and ≥80%)
- Proportion of BRV responders by time interval at evaluation periods of 0 hours to 3 hours, >3 hours to 6 hours, >6 hours to 12 hours, >12 hours to 24 hours, >24 hours to 36 hours, >36 hours to 48 hours, >48 hours to 72 hours, and >72 hours to 96 hours after the start of initial BRV treatment
- Proportion of subjects who switch over from BRV to another AED during the 96-hour Evaluation Period
- Proportion of responders to other treatment during the 96-hour Evaluation Period (including at the end of the 96-hour Evaluation Period, and by time intervals: 0 hours to 3 hours, >3 hours to 6 hours, >6 hours to 12 hours, >12 hours to 24 hours, >24 hours to 36 hours, >36 hours to 48 hours, >48 hours to 72 hours, and >72 hours to 96 hours after the start of initial BRV treatment)

(A responder to other treatment is defined as at least 80% reduction in nonsevere seizure burden from start of other treatment to end of other treatment or at least 50% reduction in severe seizure burden from the initiation of other treatment to end of other treatment during the 96-hour Evaluation Period).

4.3 Safety variables (Exploratory and Confirmatory Cohorts)

4.3.1 Secondary safety variable

The secondary safety variable is as follows:

- AEs as reported by the Investigator

4.3.2 Other safety variables

- Change from Baseline in vital signs (blood pressure, heart rate, respiratory rate [including apneas], oxygen saturation [pulse oximetry], and body temperature)
- Change from Baseline in safety laboratory tests to the end of the Evaluation Period
- Change from Baseline in heart rate at 3 hours, 24 hours, 48 hours, and 96 hours after the start of initial BRV treatment
- Change from Baseline in physical and neurological examination 24 hours, 48 hours, 72 hours, and 96 hours after the start of initial BRV treatment (Sarnat scale; for subjects with HIE only)
- Change from Baseline in EEG-parameters (assessment of sedation) to the end of the Evaluation Period (Confirmatory Cohorts only)
- Change from Baseline in severity of HIE to the end of the Evaluation Period (Thompson score; for subjects with HIE only)
- Change from Baseline in N-PASS score (neonatal pain and agitation measures) to the end of the Evaluation Period
- Change from Baseline in biometric parameters at the Safety Follow-Up Visit: length, body weight, and head circumference (head circumference Baseline measurement should be taken within 7 days prior to drug administration, or at birth for subjects \leq 7 days old)
- Withdrawal and rebound phenomena
- Mechanical ventilation:
 - Number and percentage of subjects requiring mechanical ventilation during the Evaluation Period
 - Duration of mechanical ventilation during the Evaluation Period

Neurodevelopmental tests validated for age and language will be done after 1 year for subjects who enter the long-term follow-up study in countries where a validated translation of the Bayley Scales of Infant and Toddler Development[®], Third Edition (Bayley-III[®]) score is available.

5 STUDY DESIGN

5.1 Study description

N01349 is a Phase 2/3, multicenter, open-label, single-arm study to evaluate the PK, efficacy, and safety of BRV in neonates with repeated EEG seizures.

N01349 consists of a 2-step design and includes a descriptive comparison with a historical control group (matched in age and condition) from literature treated with AEDs per SOC and diagnostic methods.

For the Exploratory Cohort (first step), enrolled subjects will have received 1 or more of following AEDs prior to or at the time of enrollment: PB, MDZ, PHT, LEV, or LDC for the treatment of ENS (first-line, second-line, or subsequent treatment; choice of treatment, dose, and dosing frequency are at the discretion of the Investigator) prior to receiving BRV. Subsequently, a low dose of BRV iv solution for injection will be administered. At the discretion of the Investigator, 3 additional iv BRV doses, up to a total of 4 iv BRV doses (0.5mg/kg bid), can be administered during the 48-hour Evaluation Period. This treatment, which is the first use of BRV in neonates, is 4-fold less than the highest dose of 4mg/kg/day dosage (2mg/kg bid) that has been used previously in infants \geq 1 month old.

For the Confirmatory Cohorts (second step), 3 consecutive cohorts are planned, and the efficacy of BRV will be evaluated. Subjects may receive 1 or more of the following AEDs prior to or at the time of enrollment: PB, MDZ, PHT, LEV (\leq 60mg/kg/day), PHT, or LDC. The iv dose of BRV selected for the Confirmatory Cohorts will be determined by the evaluation of BRV plasma concentrations from the Exploratory Cohort, as well as by previous PK modeling of N01263 data, to be within the range of plasma concentrations observed in children \geq 1 month old who received 4mg/kg/day. A dosage of BRV 4mg/kg/day for neonates is predicted to be approximately equivalent to the highest BRV dosage (200mg/day) that has been studied in the adult Phase 3 program (eg, N01358 and N01258).

The PK and safety of BRV will be evaluated in all cohorts. The recommendation to confirm or adjust the originally calculated BRV dose of the Confirmatory Cohorts of study N01349 will be given by the DMC after review of PK and safety data of the Exploratory Cohort. Based on the DMC meeting held on 05 Nov 2020, the BRV dose and frequency selected for the Confirmatory Cohorts is 1mg/kg bid (2mg/kg/day). Based on data from the Confirmatory Cohorts, the BRV dose may be further adjusted in a staggered approach as determined by the DMC.

At the end of the Evaluation Period, subjects from both the Exploratory and Confirmatory Cohorts may enter the BRV Extension Period.

All subjects who participate in the BRV Extension Period must be offered entry into a long-term study, if they meet the eligibility criteria. Before entering the long-term study, subjects must be on oral BRV.

Blood samples for routine assay of hematology, biochemistry, liver enzymes, and endocrinology will be collected in line with [Section 13.2](#) of the “Ethical Considerations for Clinical Trials on Medicinal Products Conducted with the Paediatric Population” (European Union Commission ad hoc group, 2008), and according to the schedule of study assessments in [Table 5–1](#) (Exploratory Cohort) and [Table 5–2](#) (Confirmatory Cohorts). The local laboratories will perform the routine analysis of blood samples. For Screening and determination of eligibility, use of laboratory data

acquired prior to Screening per standard of care inside or outside the study site within 36 hours prior to the start of the Evaluation Period is allowed.

Interpretation of VEEGs recorded for the Confirmatory Cohorts will be done by local readers but may be supported by the blinded central reader, as needed. Start and stop of BRV treatment and the administration of rescue medication or alternative AEDs will be digitally marked as treatment events on VEEGs. The VEEG recordings will subsequently be evaluated by a blinded, independent central reader at the end of the study. The independent central reader will be blinded from site-specific information and the subject's medical history.

Subjects assigned to the Confirmatory Cohorts will be evaluated with VEEG monitoring at least during the Baseline, Evaluation, and Down-Titration Period. Interruption of the VEEG is allowed up to 30 minutes per day. Depending on medical needs related to SOC (eg, MRIs to be performed), interruptions longer than this are acceptable. However, every effort should be made to avoid VEEG interruption of the Baseline VEEG and during the first 3 hours after the start of the initial BRV administration. The video portion of the VEEG monitoring will assist Investigators in accurately diagnosing ENS and distinguishing artifacts from epileptiform discharges/seizures.

For subjects undergoing therapeutic hypothermia treatment, the target low body temperature achieved and age since birth when cooling began will be recorded. Rewarming of subjects will be documented in the same way.

If appropriate (in the event of screening failures), re-screening will be allowed for the study. Re-screening for screen-failed subjects will be allowed with prior consultation of the Medical Monitor whenever feasible. Subjects can be re-screened only once. Once a subject has received at least one dose of BRV or has left the study because a "must withdrawal" criterion is met, re-screening will no longer be possible.

A continuous consent process will be followed. Parent(s) or legal representative(s) will be informed about the study as early as possible and asked to sign the Informed Consent form (ICF) after the occurrence of seizures has been confirmed by VEEG; subjects will then be considered to be enrolled. During the course of the study, parent(s) or legal representative(s) will be updated about the care of their neonate, and continuous consent will be ensured by meetings between the Investigator (or designee) and the subject's parent(s) or legal representative(s). Parent(s) or legal representative(s) will not be asked to re-sign and re-date the ICF, but they will be informed that they can withdraw their neonate from the study at any time and that this decision will not affect the care of their neonate. Continuous consent will be documented in the subjects' medical charts and electronic Case Report form (eCRF).

A DMC will be in place for the duration of this study. The DMC will meet after completion of the 6 subjects in the Exploratory Cohort and after completion of each of the 3 Confirmatory Cohorts (12 subjects each). Although it was planned that the DMC will meet at no longer than 6-month intervals between meetings, due to the low enrollment rate observed, the intervals between meetings may be increased per the discretion of the DMC.

The schedules of assessments during the Screening and Evaluation Periods for the Exploratory and Confirmatory Cohorts are presented in [Table 5–1](#) and [Table 5–2](#), respectively. The schedule of assessments during the BRV Extension, Down-Titration (Confirmatory Cohorts only), and

Safety Follow-Up Periods for both the Exploratory and Confirmatory Cohorts are presented in [Table 5-3](#).

Details of the study periods for the Exploratory and Confirmatory Cohorts are described in Section [5.1.1](#) and Section [5.1.2](#), respectively.

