As soon as subjects are considered to be in status epilepticus, steps required for the preparation of the initial BRV infusion can be initiated (eg, assignment of BRV kits through interactive response technology [IRT] and the dilution of BRV solution for iv infusion), even if the required EEG recording is not completed by that time.

Status epilepticus in neonates for the purpose of this study is defined as follows:

- 15 minutes of continuous or cumulative electrographic or electroclinical seizure within 30 minutes

The occurrence of ENS during the Baseline Period must be confirmed either by the local or central VEEG reader prior to BRV administration. Preferably, the central VEEG reader should confirm the required ENS. Video-EEGs that are acquired per standard of care prior to consenting and meet study-specific technical and quality requirements (eg, ability for immediate cloud-based central review) can be used as part of the Baseline assessment VEEG.

- Evaluation Period (96 hours): The first administration of BRV marks the starting point of the Evaluation Period. Subjects in the Confirmatory Cohorts will receive iv BRV 1mg/kg bid (2mg/kg/day), as recommended by the DMC on 05 Nov 2020 based on the results of the PK analysis of the Exploratory Cohort as well an existing PK model from N01263. The DMC will continue to monitor the PK and safety of the subjects and dosing may be adjusted as new data are available. If subjects do not benefit from BRV treatment after 96 hours of BRV administration, BRV administration will be stopped and replaced by another AED.

Following the first BRV infusion, 6 PK blood microsamples (60 μ L/sample) will be collected during the 96-hour Evaluation Period for each subject for the determination of plasma concentrations of BRV and its metabolites, as described in [Table 5–5](#). Blood for PK samples should be drawn from a line different to that of the BRV infusion.

The AED PK sample should be collected 3 hours after the start of the initial BRV administration. In addition, opportunistic blood samples for the PK analysis may be used at the Investigator's discretion at any time during the Evaluation Period (see [Section 9.1](#)).

At the end of the Evaluation Period, subjects who benefit from BRV treatment may enter the BRV Extension Period in accordance with the Investigator's opinion. Subjects not entering the BRV Extension Period will proceed to the Down-Titration Period.

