7.9 Blinding

This is an open-label study and, therefore, no blinding is required.

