10.3 Seizure burden

Seizure burden is defined as the total minutes of ENS per hour. Seizure burden information will be recorded for the Confirmatory Cohorts via a continuous VEEG. Seizure burden at Baseline will be evaluated over a period of at least 1 hour (subjects with intermittent seizures) or up to 30 minutes (subjects in status epilepticus).

Electroencephalographic neonatal seizures are defined as EEG seizures occurring for at least 10 seconds.

Seizure counts/seizure burden will be based on data collected using continuous VEEG. The VEEG recording will be evaluated by the local physician or central reader to evaluate eligibility of the subject. The VEEG recordings will subsequently be confirmed and quantified by the central reader at the end of the study.

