13.5 Planned efficacy analyses

All efficacy parameters will be summarized descriptively.

Video-EEGs will be assessed locally by the Investigator for any medical decisions or medical interventions. Video-EEGs may also be assessed by a blinded, central reader to support Investigators if needed. The final analysis of VEEG outputs will be based solely on the assessment of a central reader. Efficacy parameters will be summarized descriptively (overall [with CIs]) by cohort. All efficacy variables will be analyzed by the primary cause of seizure (HIE, hemorrhage, or infarction; CNS malformations; CNS infections; undetermined causes) and concomitant use of hypothermia, and reported for each subject using data listings.

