8.1.5 Percent change in baseline seizure burden

Percent change in baseline seizure burden is defined as a difference between average per hour seizure burden at baseline (calculated over the 1-hour baseline period) and average per hour

seizure burden calculated over given period of time after the start of initial BRV treatment divided by the average per hour seizure burden at baseline and multiplied by 100.

If the percent change is $\geq 80\%$ (reduction in baseline) and baseline seizure burden is non-severe or if the percent change $\geq 50\%$ (reduction in baseline) and baseline seizure burden is severe then this subject is defined as **BRV responder**. No rounding will be applied, one decimal will be considered for comparison (for example, if the percent change is 79.999%, then consider 1 decimal as 79.9% which is less than 80%).

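### The stated blind of the central VEEG reader leaves out treatment events that are marked on the recordings, so the final seizure-burden read is not protected from knowledge of time relative to BRV and rescue

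*Protocol*

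**What the plan says.** Protocol 5.1 makes three statements in succession. Treatment events go on the recording: "Start and stop of BRV treatment and the administration of rescue medication or alternative AEDs will be digitally marked as treatment events on VEEGs". The recordings are then read: "The VEEG recordings will subsequently be evaluated by a blinded, independent central reader at the end of the study". The blind is defined: "The independent central reader will be blinded from site-specific information and the subject's medical history". BRV, rescue, other AEDs and time relative to first dose are not in that definition.

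Protocol 10.3 gives the same reader the quantification: "The VEEG recordings will subsequently be confirmed and quantified by the central reader at the end of the study". Protocol 13.5 makes it decisive for the VEEG data: "The final analysis of VEEG outputs will be based solely on the assessment of a central reader".

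The central reader may also see a baby's recording before dosing. Protocol 5.1.2 says of Baseline seizures: "Preferably, the central VEEG reader should confirm the required ENS".

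On blinding in general, Protocol 7.9 says only: "This is an open-label study and, therefore, no blinding is required". The SAP adds no reading procedure. Its section 8.1.5 builds response on the "difference between average per hour seizure burden at baseline" and the burden over a post-dose period, as a percentage of Baseline.

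**The concern.** In a single-arm, open-label study with a within-baby endpoint, the contrast most in need of masking at the read is before versus after drug. Hiding site and history removes some cues, but does little for that contrast. Scoring involves judgement: the reader has to separate seizure from artefact, apply the 10-second minimum and decide where a discharge starts and stops. A reader who knows that a segment follows BRV may, without intending to, score it differently from Baseline, and no concurrent arm read in the same way would cancel the difference.

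At stake is the responder rate for the main secondary variable. Protocol 13.5.1 compares its 95% confidence interval with a historical responder rate and calls BRV efficacious relative to that control if the lower limit is above it.

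**Working it through.** The plan gives no figure to reproduce: Protocol 13.9 states that no formal sample size calculation was done. The check therefore has a textual part and an arithmetic part that shows scale only.

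**Text.** Markers are placed on the VEEGs (5.1). The reader evaluates and quantifies the VEEG recordings (5.1, 10.3). The blind lists two items, neither of them treatment or time (5.1). No section of either document provides for removing markers, coding segments, randomising reading order, or separating the eligibility reader from the final reader.

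**Sensitivity of one baby's status.** Inputs: entry needs at least 2 minutes of cumulative ENS or at least 3 ENS of 10 seconds or more (Protocol 6.1); a nonsevere responder needs at least an 80% reduction over a 2-hour window (Protocol 4.2.1); no rounding is applied (SAP 8.1.5).

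Formula: reduction = 100 × (B − E/2)/B, with B the Baseline burden in seconds per hour and E the seconds of ENS in the 2-hour window. The largest E that keeps response is 0.20 × B × 2.

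- Minimum entry burden through the count route, with a 1-hour Baseline: B = 3 × 10 = 30 s/h. Allowance 0.20 × 30 × 2 = 12 s.
  - One 10-second ENS: (30 − 5)/30 = 83.3%, responder.
  - Two: (30 − 10)/30 = 66.7%, nonresponder.
  - One event timed at 13 seconds: (30 − 6.5)/30 = 78.3%, nonresponder.
- B = 120 s/h (2 min/h): allowance 0.20 × 120 × 2 = 48 s. Four 10-second ENS give (120 − 20)/120 = 83.3%; five give (120 − 25)/120 = 79.2%.
- Severe Baseline of, for example, 20 min/h under the 50% rule: allowance 0.50 × 20 × 2 = 20 minutes. One 10-second call will rarely matter.

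**Effect on the rate.** With the planned minimum of 36 babies all analysed, one changed status moves the rate by 1/36 = 2.8 percentage points.

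**Effect on the 13.5.1 rule, as illustration.** The documents give neither the historical rate nor the interval method. Assumed here: historical rates p0 of 0.20 to 0.60, exact (Clopper-Pearson) limits, n = 36, a true BRV rate equal to p0, and a fraction m of true nonresponders misread as responders, with no errors the other way. The observed rate is then p0 + (1 − p0) × m. The last three columns give the chance that BRV is called efficacious.

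| p0 | Responders needed | Lower limit | Lower limit, one fewer | m = 0 | m = 5% | m = 10% |
|---|---|---|---|---|---|---|
| 0.20 | 13 | 0.208 | 0.186 | 1.8% | 7.0% | 18.3% |
| 0.30 | 17 | 0.304 | 0.279 | 2.2% | 6.1% | 13.7% |
| 0.40 | 21 | 0.408 | 0.381 | 2.0% | 4.6% | 9.4% |
| 0.50 | 25 | 0.519 | 0.490 | 1.4% | 3.0% | 5.6% |
| 0.60 | 28 | 0.608 | 0.578 | 2.0% | 3.4% | 5.7% |

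The values of m are not estimates; nothing in the documents gives a reader-error rate or its direction.

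**The case against.** The strongest reply is that nothing here is contradictory. Protocol 5.1 says what the blind covers, 7.9 says the study is open-label, and a separate reading manual may already suppress the markers. A reader might infer that the central reader is shown the markers and knows the status of every segment. The documents do not say so; they say that the markers are placed and that no masking is described. The objection stands to that extent: the point concerns missing protection, not demonstrated unblinding.

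Two further inferences would go too far.

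- That the central reader alone decides efficacy. Responder status also depends on rescue, AED increase or AED switch in the first 3 hours (Protocol 10.1), and in SAP 8.1.1 on dropout for lack of efficacy. Only the seizure-burden part rests solely on the reader.
- That every efficacy variable is a change from Baseline. Switching to another AED (SAP 8.3.1) and seizure freedom at the end of Down-Titration (SAP 8.2.4) are not.

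It is also fair to say that the 30 s/h example is a floor case, that the primary objective is PK and is untouched, and that SAP 4.5 calls all analyses descriptive. The last argument only partly helps, because Protocol 13.5.1 still contains a rule that ends in a statement about efficacy.

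Finally, hiding markers cannot mask everything. The video may show infusions, and the central reader may already have confirmed that baby's Baseline seizures. This limits what the fix achieves; it does not remove the reason for it.

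**Conclusion.** The point holds as a gap in the stated blind, and it should be fixed. The plan calls the reader blinded but does not protect that reader from knowing whether a segment is before BRV, after BRV or after rescue, although the main secondary variable depends on that contrast.

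The size is bounded rather than known. Near the minimum entry burden one 10-second call can change responder status, and each change is worth 2.8 points at n = 36. At heavier Baselines the sensitivity falls quickly. The documents give no distribution of Baseline burden, so the number of fragile babies cannot be stated. In the illustration, 5% one-way misreading raises the chance of a false efficacy statement from between 1.4% and 2.2% to between 3.0% and 7.0%; that rests on assumed historical rates, interval method and misread rates.

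The documents do not support a claim that the efficacy result is in fact biased, or that the trial's primary purpose is compromised.

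**What to change.** In Protocol 5.1, 10.3 and 13.5, state that:

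- treatment-event markers and clock time are removed or hidden on the copy used for the final central read;
- the Baseline and 0 to 3 hour segments needed for the main secondary variable are presented under coded labels in random order, where feasible;
- event times stay in the database, and scored ENS are assigned to Baseline, post-dose and post-rescue windows by timestamp after the read is locked;
- where the central-reading service already has more than one reader, whoever confirmed a baby's eligibility does not do that baby's final read.

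The cost is an export step and some text on reading procedure; no patient, visit or treatment changes. The downsides are that some segments are read out of sequence and that masking stays incomplete, because the video may show infusions and the later time points still need the full recording. Since the final read takes place at the end of the study, acting before it avoids a re-read.

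If the markers are already hidden, one sentence in 5.1 and 13.5 settles the matter. If they are to stay visible, describe the reader as blinded to site and medical history only, and report this as a limitation of the historical-control comparison.
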